1. PROTOCOL SUMMARY

1.1. Synopsis

A Phase 1, open label, fixed sequence study to estimate the effect of multiple dose PF-06650833 on the pharmacokinetics of single dose oral contraceptive steroids in healthy female participants.

Brief Title: A Phase 1 Drug-Drug Interaction Study of PF-06650833 With Oral Contraceptives in Healthy Female Participants

Rationale

This study will evaluate the effect of PF-06650833 on pharmacokinetics of OC steroids, in order to select appropriate contraception requirements in Phase 2 studies. **CCI** [REDACTED]

Objectives and Endpoints

Objectives	Endpoints
Primary:	Primary:

To estimate the effect of multiple oral doses of PF-06650833 on the PK of a single dose of a combination OC in healthy female participants.	
C_{max} and AUC_{last} of EE and LN.
Secondary:	Secondary:

To evaluate the safety of PF-06650833 when co-administered with a single dose of a combination OC in healthy female participants.	
Safety: laboratory tests, AEs reporting and vital signs.
Tertiary/Exploratory:	Tertiary/Exploratory:

To characterize the PK of a single dose of a combination OC with or without PF-06650833 in healthy female participants.	
T_{max}, and if data permit CL/F, $t_{1/2}$ and AUC_{inf}, of EE and LN.

Overall Design

Brief Summary

This is a Phase 1, fixed-sequence, multiple-dose, open-label study of the effect of multiple dose PF-06650833 on single dose OC PK in healthy female participants. The study will consist of 2 periods in a single fixed sequence. Participants will be screened within 28 days of the first dose of investigational product in Period 1. Participants will report to the CRU the

day prior to Day 1 dosing in Period 1. Participants will remain in the CRU for a total of 16 days and 15 nights. There will be no washout period.

PF-06650833 is not expected to provide any clinical benefit to healthy participants. This study is designed primarily to generate safety, tolerability, and PK data for further clinical development.

Number of Participants

Approximately 10 participants will be enrolled to study intervention.

Note: “Enrolled” means a participant’s, or his or her legally authorized representative’s, agreement to participate in a clinical study following completion of the informed consent process and screening. A participant will be considered enrolled if the informed consent is not withdrawn prior to participating in any study activity after screening. Potential participants who are screened for the purpose of determining eligibility for the study, but do not participate in the study, are not considered enrolled, unless otherwise specified by the protocol.

Intervention Groups and Duration

The current study will use a PF-06650833 dose of 400 mg MR QD. This is the highest dose of PF-06650833 planned for use in future efficacy and safety trials.

On Period 1 Day 1, participants will be dosed with a single administration of OC in the form of 1 PORTIA® (EE and LN) or equivalent tablet, orally. OC (EE and LN) PK will then be assessed at pre-dose and over 48 hours, post OC dosing. Period 1 will be immediately followed by Period 2 with no washout, in which participants will be dosed orally with PF-06650833 400 mg MR QD for 9 days followed by administration of a single dose of OC on the morning of Day 10. OC PK will be assessed at pre-dose and for 48 hours following OC dosing. The 48 hours post OC dose PK sample must be collected prior to receiving first dose of PF-06650833. On Day 10, the morning dose of PF-06650833 and the single OC dose will be administered simultaneously within 5 minutes. Dosing with PF-06650833 400 mg PO QD will continue until Day 11.

Data Monitoring Committee or Other Independent Oversight Committee

[figure not shown]
No

Statistical Methods

To assess any effect of PF-06650833 on EE or LN exposures, natural log transformed AUC_{last} and C_{max} will be analyzed using a mixed effects model with treatment as a fixed effect and participant as a random effect. Estimates of the adjusted mean differences (Test-Reference) and corresponding 90% CIs will be obtained from the model and will be

exponentiated to provide estimates of the ratio of adjusted geometric means (Test/Reference) and 90% CIs for the ratios.

1.2. Schema

1.3. Schedule of Activities

The SoA table provides an overview of the protocol visits and procedures. Refer to the **STUDY ASSESSMENTS AND PROCEDURES** section of the protocol for detailed information on each procedure and assessment required for compliance with the protocol.

The investigator may schedule visits (unplanned visits) in addition to those listed in the SoA table, in order to conduct evaluations or assessments required to protect the well-being of the participant.

	Screening	Period 1				Period 2 ^m						Early Termination/Discontinuation	Follow-up ⁿ
Visit Identifier ^a Abbreviations used in this table may be found in Appendix 8	Day -28 to Day -2	Day -1	Day 1	Day 2	Day 3	Day 1	Day 2 to Day 8	Day 9	Day 10	Day 11	Day 12		28-35 days after last dose
Informed consent	X												
CRU confinement		X	→	→	→	→	→	→	→	→	X		
Inclusion/exclusion criteria	X	X											
Medical, drug, tobacco and alcohol history	X	X											
Contraception check	X	X										X	X
Pregnancy test (for WOCBP)	X	X										X	
Demography	X												
Physical examination ^b	X	X											
Safety laboratory	X	X						X		X	X		
TB Screen ^c	X												
Serum FSH (postmenopausal women only)	X												
Serology: Viral screen, HBsAg, HCVAb, HIV, HBsAb and HBcAb	X												
CCI			█										
Urine drug screen	X	X											
12-Lead ECG (single)	X		X							X	X		
Vital signs (supine BP, pulse rate) ^e	X		X			X			X		X	X	
COVID-19 questionnaire ^f	X	X											
COVID-19 testing ^g	X	X											
COVID-19 check temperature ^h	X	X	→	→	→	→	→	→	→	→	X	X	

PFIZER CONFIDENTIAL

	Screening	Period 1				Period 2 ^m						Early Termination/Discontinuation	Follow-up ⁿ
Visit Identifier ^a Abbreviations used in this table may be found in Appendix 8	Day -28 to Day -2	Day -1	Day 1	Day 2	Day 3	Day 1	Day 2 to Day 8	Day 9	Day 10	Day 11	Day 12		28-35 days after last dose
OC dosing ⁱ			X						X				
PF-06650833 QD dosing ^j						X	X	X	X	X			
OC PK blood sample ^{k,l}			X	X	X				X	X	X	X	
Serious and non-serious AE monitoring	X	→	→	→	→	→	→	→	→	→	→	X	X
Prior/concomitant treatment assessment	X	→	→	→	→	→	→	→	→	→	→	X	X
CRU discharge												X	

- a. **Visit Identifier:** Day relative to start of study treatment (Day 1).
- b. **Physical Examination:** Complete physical exam could be done at screening or admission on Day -1. Brief physical exam to be done only in case of finding at previous exam or new/open AE if applicable, at the discretion of the investigator.
- c. **TB Screen:** QFT-G test.
- d. **COVID-19 screening:** COVID-19 screening will be done at screening and Day -1. A subsequent COVID-19 test can be performed if participants admitted for residence develop COVID-19 like symptom(s).
- e. **Vital signs (supine BP, pulse rate):** Vital signs will be collected before dosing.
- f. **COVID-19 questionnaire:** Check exposure to positive participant, residence or travel in area of high incidence and COVID-19 related signs and symptoms.
- g. **COVID-19 testing:** The testing for COVID-19 pathogen by PCR will be performed screening and D-1. A subsequent COVID-19 test can be performed if participants admitted for residence develop COVID-19 like symptom(s).
- h. **COVID-19 check temperature:** To be done twice daily during residence.
- i. **OC dosing:** Participants will be dosed with OC following an overnight fast of at least 10 hours. On the day of co-administration of OC and PF-06650833, the two will be administered simultaneously within 5 minutes.
- j. **PF-06650833 QD dosing:** The daily dose of PF-06650833 will be administered at approximately 08:00 ±2 hours.
- k. **OC PK blood sample:** PK blood samples are to be collected at predose, at 30 minutes and 1, 1.5, 2, 4, 6, 8, 12, 24, 36 and 48 hours post OC dose in Periods 1 and 2.
- l. **OC PK blood sample:** The 24 hour OC PK samples on Period 2 Day 11 must be collected pre PF-06650833 dose.
- m. **Period 2:** There is no washout phase between Period 1 and Period 2.
- n. **Follow-up:** Participants will have a telephone contact at least 28 calendar days, and up to 35 calendar days after the last administration of the investigational product(s). At the discretion of the investigator, telephone contact may be substituted with an on-site visit in case of additional follow-up of open AEs or clinically significant laboratory findings

2. INTRODUCTION

PF-06650833 is a selective and reversible inhibitor of IRAK4 which is under clinical development as a potential treatment for RA, HS, COVID-19 and acne vulgaris.

2.1. Study Rationale

This study will evaluate the effect of PF-06650833 on pharmacokinetics of OC steroids, in order to select appropriate contraception requirements in Phase 2 studies. **CCI** [REDACTED]

CCI [REDACTED]

[REDACTED]

[REDACTED]

The metabolism of OC steroids such as EE and LN, is mediated by the CYP3A and Phase 2 enzymes such as UGT and SULT. Induction of the metabolic enzymes involved in metabolism of OC's may result in reduction in the systemic exposure of these hormonal contraceptives leading to a potential failure of contraception. Therefore, the current study is designed to estimate the effect of multiple dose of PF-06650833 on the PK of 2 commonly concomitantly administered OCs, EE and LN.

2.2. Background

[figure not shown]
2.2.1. Nonclinical Pharmacology

PF-06650833 is a highly selective inhibitor of IRAK4 with nanomolar potency both in recombinant enzyme assays and in cellular assays. PF-06650833 inhibits IRAK4 with low nmol/L ($IC_{50} < 5$ nmol/L) potency in cell based assays of TLR-mediated cytokine induction. In the rat CIA model, PF-06650833 dosed orally at 3 to 100 mg/kg BID or 30 and 100 mg/kg QD significantly reduced hind paw swelling.

[figure not shown]
[figure not shown]
CCI

CCI

CCI

2.2.4. Clinical Overview

As of the date of this protocol, PF-06650833 has been evaluated in 7 completed Phase 1 studies (B7921001, B7921002, B7921004, B7921006, B7921011, B7921009 and B7921028) and 1 completed Phase 2 study in RA patients (B7921005) and 3 ongoing Phase 2 studies in patients with RA (B7921023), HS (C2501007) and COVID-19 with ARDS (I-RAMIC).

Study B7921001 and B7921002 were SAD and MAD studies in healthy participants, respectively. B7921004 and B7921011 were relative bioavailability studies. B7921009 was a mass balance study while B7921006 was multiple dose PK and safety assessment in Japanese participants.

CCI

In all of the completed Phase 1 and Phase 2 studies, PF-06650833 was generally well tolerated and no maximally tolerated dose has been established. No deaths or other SAEs occurred in any of the studies. The most commonly observed AEs were headache and AEs within the SOC of 'GI disorders' (diarrhoea, abdominal discomfort, abdominal distension, abdominal pain, dry mouth, enterocolitis and flatulence). All TEAEs were mild to moderate in severity. CCI

Summary of Clinical PK

In Studies B7921001 and B7921002, PF-06650833 exposure (AUC and C_{max}) increased in a dose related manner up to the 100 mg dose, with less-than-proportional increases observed at higher doses. Accumulation ranged from 0.9-fold to 1.4-fold for AUC_{tau} and 0.9 fold to 1.3 fold for C_{max} . Less than 1% of the dose was recovered unchanged in urine.

CCI

[figure not shown]

2.3. Benefit/Risk Assessment

PF-06650833 is not expected to provide any clinical benefit to healthy participants. This study is designed primarily to generate safety, tolerability, and pharmacokinetic data for further clinical development.

[figure not shown]
In the clinical studies of PF-06650833 (see [Section 2.2.4](#)), the investigational product was determined to be well tolerated and to have an acceptable safety profile.

CCI

More detailed information about the known and expected benefits and risks and reasonably expected AEs of PF-06650833 may be found in the IB, which is the SRSD for this study.

The expected exposures of PF-06650833 in this study are lower than the highest exposures observed in the Phase 1 studies (see Justification for Dose in [Section 4.3](#)). CCI

herefore, the risk to the participants in this study is expected to be minimal. In addition, any risks are minimized by appropriate safety measures including safety laboratory measurements, ECGs, vital signs for study participants.

2.3.1. Risk Assessment

Potential Risk of Clinical Significance	Summary of Data/Rationale for Risk	Mitigation Strategy
Study Intervention(s): PF-06650833		
		
Other		
The COVID-19 pandemic may pose risks to study participation.	Participants may have increased risk of SARS-CoV-2 infection by undergoing a study procedure at a study facility.	Inclusion of COVID-19 specific assessments according to the Schedule of Activities and CRU confinement for the entire duration of study.

2.3.2. Benefit Assessment

There is no benefit expected to the participants.

2.3.3. Overall Benefit/Risk Conclusion

PF-06650833 is not expected to provide any clinical benefit to healthy participants. Study in healthy participants is justified by taking into account the measures to minimize potential risk.

3. OBJECTIVES AND ENDPOINTS

Objectives	Endpoints
Primary: 
To estimate the effect of multiple oral doses of PF-06650833 on the PK of a single dose of a combination OC in healthy female participants.	Primary: 
C_{max} and AUC_{last} of EE and LN.
Secondary: 
To evaluate the safety of PF-06650833 when co-administered with a single dose of a combination OC in healthy female participants.	Secondary: 
Safety: laboratory tests, AEs reporting and vital signs.
Tertiary/Exploratory: 
To characterize the PK of a single dose of a combination OC with or without PF-06650833 in healthy female participants.	Tertiary/Exploratory: 
T_{max}, and if data permit CL/F, $t_{1/2}$ and AUC_{inf}, of EE and LN.

4. STUDY DESIGN

4.1. Overall Design

This is a Phase 1, fixed-sequence, multiple-dose, open-label study of the effect of multiple dose PF-06650833 on single dose OC PK in healthy female participants. A total of approximately 10 healthy female participants will be enrolled in the study. The study will consist of 2 periods in a single fixed sequence. Participants will be screened within 28 days of the first dose of investigational product in Period 1. Participants will report to the CRU the day prior to Day 1 dosing in Period 1. Participants will remain in the CRU for a total of 16 days and 15 nights. There will be no washout period.

On Period 1 Day 1, participants will be dosed with a single administration of OC in the form of 1 PORTIA® (EE and LN) or equivalent tablet, orally. OC (EE and LN) PK will then be assessed at pre-dose and over 48 hours, post OC dosing. Period 1 will be immediately followed by Period 2 with no washout, in which participants will be dosed orally with PF-06650833 400 mg MR QD for 9 days followed by administration of a single dose of OC on the morning of Day 10. OC PK will be assessed at pre-dose and for 48 hours following OC dosing. On Day 10, the morning dose of PF-06650833 and the single OC dose will be

administered simultaneously within 5 minutes. Dosing with PF-06650833 400 mg PO QD will continue until Day 11 (Table 1). Participants will be discharged on Day 12 only after review of safety laboratory by the PI.

Table 1. Study Design and Treatments

Period 1	Washout	Period 2
Treatment A	None	Treatment B

Treatment A: Single dose of OC in the form of 1 PORTIA® (EE and LN) or equivalent oral tablet, containing EE 30 µg and LN 150 µg.

Treatment B: Single dose of combination OC in the form of 1 PORTIA® (EE and LN) or equivalent oral tablet, containing of EE 30 µg and LN 150 µg on the morning of Day 10 following 9 days of PF-06650833 dosed at 400 mg PO QD. Dosing with PF-06650833 at 400 mg PO QD will continue through until Day 11.

4.2. Scientific Rationale for Study Design

Given the potential teratogenicity risk of PF-06650833 and potential of CYP3A induction risk, only WONCBP will be allowed in this study.

A fixed sequence design was selected for this study over a randomized 2-sequence crossover design based on operational considerations. It should be noted that the fixed sequence study design does not control for a period effect, however, the period effect is generally considered to be a low risk for PK DDI studies.

Based on the in vitro metabolic profiling, there is low potential of oral contraceptive steroids to impact PK of PF-06650833, only the effect of PF-06650833 will be evaluated in this study. In order to allow the full effect of potential enzyme induction of CYP3A4 to manifest, PF-06650833 will be dosed for 10 days prior to OC dosing. This is supported by Simcyp simulations showing maximal induction of CYP3A4 by PF-06650833 under the study design.

Due to the effect of food on PK of PF-06650833 MR and consistent with Phase 2 studies, PF-06650833 will be dosed in fasted state in this study.

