4.2.2. Choice of Contraception/Barrier Requirements

CCI

[REDACTED] therefore, the use of a highly effective method of contraception is required (see [Appendix 4](#)).

[figure not shown]
CCI

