5.1. Inclusion Criteria

Participants are eligible to be included in the study only if all of the following criteria apply:

Age and Sex:

1. Healthy female participants who, at the time of screening, are between the ages of 18 and 60 years, inclusive. Healthy is defined as no clinically relevant abnormalities identified by a detailed medical history, full physical examination, including BP and pulse rate measurement, 12-lead ECG, or clinical laboratory tests.
2. Female participants of non-childbearing potential must meet at least 1 of the following criteria:
 - a. Achieved postmenopausal status, defined as follows: cessation of regular menses for at least 12 consecutive months with no alternative pathological or physiological cause; and have a serum FSH level confirming the postmenopausal state;
 - b. Have undergone a documented hysterectomy and/or bilateral oophorectomy and/or bilateral salpingectomy;
 - c. Have medically confirmed ovarian failure.

All other female participants (including female participants with tubal ligations) are considered to be of childbearing potential. Refer to [Appendix 4](#): Contraceptive and Barrier Guidance for reproductive criteria for female ([Section 10.4.2](#)) participants.

3. Participants who are willing and able to comply with all scheduled visits, treatment plan, laboratory tests, lifestyle considerations, and other study procedures.

Weight:

4. BMI of 17.5 to 30.5 kg/m²; and a total body weight >50 kg (110 lb).

Informed Consent:

5. Capable of giving signed informed consent as described in [Appendix 1](#), which includes compliance with the requirements and restrictions listed in the ICD and in this protocol.

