10.4.2. Female Participant Reproductive Inclusion Criteria

A female participant is eligible to participate if she is not pregnant or breastfeeding, and at least 1 of the following conditions applies:

- Is not a WOCBP (see definitions below in [Section 10.4.3](#)).

OR

- Is a WOCBP and using a contraceptive method that is highly effective (with a failure rate of <1% per year), with low user dependency, as described below during the intervention period and for at least 28 days or 5 terminal half-lives plus 14 days (whichever duration is longer) after the last dose of study intervention, which corresponds to the time needed to eliminate any reproductive safety risk of the study intervention. The investigator should evaluate the effectiveness of the contraceptive method in relationship to the first dose of study intervention.

A WOCBP agrees not to donate eggs (ova, oocytes) for the purpose of reproduction during this period. The investigator should evaluate the effectiveness of the contraceptive method in relationship to the first dose of study intervention.

The investigator is responsible for review of medical history, menstrual history, and recent sexual activity to decrease the risk for inclusion of a woman with an early undetected pregnancy.

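### Section 4.2 admits only women of non-childbearing potential, but criterion 2 does not say so plainly and section 10.4.2 makes some women of childbearing potential eligible

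*Protocol*

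**What the plan says.** Section 4.2 of the protocol sets the population rule and gives its reasons: "Given the potential teratogenicity risk of PF-06650833 and potential of CYP3A induction risk, only WONCBP will be allowed in this study".

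Section 5.1 opens its list with "Participants are eligible to be included in the study only if all of the following criteria apply". Criterion 2 then reads "Female participants of non-childbearing potential must meet at least 1 of the following criteria" and lists three categories: (a) postmenopausal; (b) hysterectomy, bilateral oophorectomy or bilateral salpingectomy; (c) medically confirmed ovarian failure. It continues: "All other female participants (including female participants with tubal ligations) are considered to be of childbearing potential", and refers the reader to Appendix 4, section 10.4.2, for the reproductive criteria.

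Section 10.4.2 says: "A female participant is eligible to participate if she is not pregnant or breastfeeding, and at least 1 of the following conditions applies". The first condition is not being a WOCBP. The second, joined by OR, is: "Is a WOCBP and using a contraceptive method that is highly effective (with a failure rate of <1% per year), with low user dependency". That contraception must continue for a period after the last dose, "which corresponds to the time needed to eliminate any reproductive safety risk of the study intervention".

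Other sections also provide for WOCBP. Section 4.2.2 says "the use of a highly effective method of contraception is required", after redacted words that may limit its scope. Section 5.3.4 requires contraception counselling without naming a subgroup. Section 8.2.6 and the Schedule of Activities provide pregnancy tests for WOCBP, and section 10.4.4 lists permitted methods.

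**The concern.** Section 4.2 closes the study to WOCBP, and section 10.4.2 opens it to some of them. The reason given for closing it includes possible teratogenicity, so this is a rule that protects participants. Sites normally screen from the numbered criteria and the appendix those criteria cite, not from a rationale paragraph. Waivers of entry criteria are not permitted (section 5), so the written criteria decide who enters, and here they allow two answers.

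What is at stake is that a woman could be given up to 11 daily 400 mg doses of PF-06650833 under one section although another says she must not be in the study. Two investigators acting in good faith could also reach opposite decisions about the same woman.

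**Working it through.** No arithmetic applies. The check takes one woman through the eligibility text: healthy, premenopausal, within the age range, not pregnant or breastfeeding, with a tubal ligation, and meeting every other criterion.

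| Place in the protocol | What it does with her |
|---|---|
| 4.2 | Bars her: she is not of non-childbearing potential |
| 5.1, criterion 1 | Admits her: healthy female aged 18 to 60 |
| 5.1, criterion 2, categories (a) to (c) | She meets none of them |
| 5.1, criterion 2, closing text | Classes her as of childbearing potential and refers to 10.4.2 |
| 5.2 | No exclusion applies; number 13 covers only pregnancy and breastfeeding |
| 10.4.3 | Tubal ligation is not among the surgical reasons for not being a WOCBP |
| 10.4.4 | Lists bilateral tubal occlusion as a highly effective method with low user dependency |
| 10.4.2 | Eligible by the second condition |

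The outcome turns on how criterion 2 is read.

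1. **As a condition on everyone.** The lead-in says all criteria must apply. She meets none of (a) to (c), so she is not eligible. This agrees with 4.2. It leaves the second condition of 10.4.2 unable to admit anyone, and leaves criterion 2 pointing to it for no purpose.
2. **As a definition.** The sentence says what women of non-childbearing potential must meet. She is not one of them, so it asks nothing of her, and she is passed to 10.4.2, which makes her eligible. This contradicts 4.2.

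The first reading is the better one: it respects the lead-in and matches 4.2. The second is still open on the wording, and 10.4.2 is titled as a set of inclusion criteria. The redaction in 4.2.2 does not resolve this, because the relevant text of 10.4.2 is fully visible.

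**Effect on the analysis.** The PK concentration, PK parameter, evaluable and safety sets are defined by dosing and available data, not by childbearing potential (protocol 9.2 and 9.3.1; SAP section 4). Each woman is her own control in the comparison of treatments. The primary endpoints and the mixed model are the same whichever reading a site adopts.

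**The case against.** The strongest reply is that the protocol already excludes these women. The lead-in makes every criterion compulsory, criterion 2 lists only non-childbearing categories, it expressly places tubal ligation outside them, and 4.2 leaves no doubt about intent. A restriction written as an inclusion criterion need not be repeated as an exclusion, so the silence of section 5.2 proves little. A site that enrols only women of non-childbearing potential complies with both 4.2 and 10.4.2. Some of the contraception text also looks generic: section 5.3.4 of this all-female study refers to partners of either sex.

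Most of this stands, and it makes the non-childbearing reading the probable intent. It does not remove the conflict, because 10.4.2 declares a WOCBP eligible in plain terms and criterion 2 directs the reader there. The documents nowhere say that the WOCBP text is left over from a template.

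A reader might go further and infer that WOCBP would be dosed without protection. The documents do not support that. The 10.4.2 route itself requires contraception with a failure rate below 1% per year, during dosing and for a stated period afterwards. The Schedule of Activities places pregnancy tests at screening and Day -1, and section 8.2.6 requires a negative result before dosing and a further test at the end of the study. Contraception checks continue to follow-up, a positive test stops the product (section 7.1.4), and all PF-06650833 doses are given in confinement. These safeguards reduce the hazard, but they do not make the two sections agree: 4.2 chose to exclude WOCBP, not to manage the risk in them.

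**Conclusion.** The inconsistency is real and is in the current text. Section 4.2 bars all WOCBP; one of the two routes in section 10.4.2 admits those on suitable contraception; and criterion 2, which probably sides with 4.2, is not worded firmly enough to settle the matter. It should be fixed as a safety-eligibility inconsistency.

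It is not a flaw in the design or the analysis, and nothing here suggests that the estimated interaction would be biased. The documents give no basis for estimating how many WOCBP might be enrolled or what their pregnancy risk would be, so neither is claimed. The conclusion assumes only that a site may act on 10.4.2 as written. That the sections conflict is certain; that the sponsor intended 4.2 to prevail is likely but not stated.

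**What to change.** - **Criterion 2 (5.1):** reword to say that every participant must be of non-childbearing potential and meet at least 1 of (a), (b) or (c).
- **10.4.2:** delete the branch that makes a WOCBP eligible.
- **4.2.2, 5.3.4 and 10.4.4:** align the contraception wording with that rule.
- **Keep** the pregnancy tests in the Schedule of Activities and section 8.2.6 as a backstop for a woman whose status has been misclassified. They are now labelled for WOCBP only, so state who is tested once all participants are meant to be of non-childbearing potential.
- **Keep** exclusion 13 and the pregnancy and breastfeeding exposure-reporting sections.

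If the sponsor did intend to admit WOCBP on contraception, it should instead correct section 4.2, justify the change against the teratogenicity and induction risks named there, and reword criterion 2 to match.

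The cost of the main fix is a protocol amendment or clarification letter. Sample size, schedule and analysis do not change. The recruitment pool is no narrower than section 4.2 already makes it.
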